16.5 Public disclosure

The results of this trial will be publically disclosed in accordance with the sponsor's disclosure policy, the European Federation of Pharmaceutical Industries and Associations (EFPIA) Principles for Responsible Clinical Trial Data Sharing and applicable regulatory guidance (e.g., on ClinicalTrials.gov).

The results (or parts thereof) of this trial may be published as a publication (e.g., journal publication) or at a congress (e.g., as a poster or presentation). The sponsor reserves the right to review any proposed full publication or poster or presentation of the results of this trial by the coordinating or other investigator before they are submitted for publication or public disclosure.

Neither the sponsor nor the coordinating investigator has the right to prohibit publication or public disclosure. Publication or public disclosure can be postponed for patent purposes.

16.6 Trial results reporting

A final report integrating clinical, pharmacokinetic, pharmacodynamic, and statistical results will be prepared by the sponsor. The international coordinating investigator will approve the final report on behalf of the participating investigators.

The sponsor will provide the competent authority/ies and relevant IECs or IRBs with a summary of the trial results in accordance with applicable regulatory requirements.

All principal investigators will be provided with a summary of the trial results.

All entered subjects will be provided access to a summary of the trial results in a lay-understandable form.

Adrenocortical insufficiency acute		
Eye disorders		
Cataract/lens opacity	Glaucoma	Keratitis/corneal opacification
Macular degeneration	Optic neuropathy, atrophy	Papilloedema
Ptosis	Retinal artery/vein occlusion	Retinitis
Scotoma	Sudden visual loss	Uveitis
Vitreous detachment		
Gastrointestinal disorders		
Colitis haemorrhagic	Gastric ulcer haemorrhage	Gastric ulcer perforation
Haematemesis	Haemoperitoneum	Ileus
Intestinal ischaemia	Intestinal perforation	Melaena
Mesenteric occlusion	Mesenteric vein thrombosis	Pancreatitis
Peritonitis		
General disorders and administration site conditions		
Malignant hyperthermia		

Hepatobiliary disorders		
Hepatic failure	Hepatitis fulminant	Hepatic necrosis
Hepatorenal syndrome	Portal hypertension	Reye's syndrome
Immune system disorders		
Amyloidosis	Anaphylactic reaction	Anaphylactic shock
Graft versus host disease		
Infections and infestations		
Endotoxic shock	Sepsis	Toxic shock syndrome
Transmission of an infectious agent via a medicinal product		
Injury, poisoning and procedural complications		
Transplant failure	Wound dehiscence	
Metabolism and nutrition disorders		
Diabetic coma	Failure to thrive	Hypercalcaemia (CTC IV)
Hyperkalaemia (CTC IV)	Hypocalcaemia (CTC IV)	Hypokalaemia (CTC IV)
Lactic acidosis	Porphyria	Shock hypoglycaemic
Tetany		
Musculoskeletal and connective tissue disorders		
Aseptic necrosis bone	Fracture pathological	Muscle necrosis
Osteomalacia	Rhabdomyolysis	Systemic lupus erythematosus
Systemic sclerosis		
Nervous system disorders		
Amnesia	Anticholinergic syndrome	Aphasia
Cerebral oedema	Chorea	Coma
Convulsions	Demyelination	Encephalitis
Encephalopathy	Epilepsy	Guillain-Barré syndrome
Hydrocephalus	Intracranial haemorrhage	Meningitis
Multiple sclerosis	Myasthenia gravis	Myelitis
Neuroleptic malignant syndrome	Opisthotonus	Paralysis
Paresis	Parkinson's syndrome	Serotonin syndrome
Stroke	Tunnel vision	
Pregnancy, puerperium and perinatal conditions		
Abortion	Eclampsia	Intra-uterine death
Psychiatric disorders		
Anorexia nervosa	Delirium	Drug abuse
Drug dependence	Homicidal ideation	Intentional misuse
Self-injurious ideation/attempt	Suicidal ideation/attempt	Suicide completed

Renal and urinary disorders

Anuria	Goodpasture's syndrome	Haemolytic uraemic syndrome
Nephritis/nephritic syndrome	Nephrotic syndrome	Oliguria
Renal failure acute	Renal tubular necrosis	Urinary obstruction/retention

Reproductive system and breast disorders

Metrorrhagia/uterine haemorrhage	Priapism
----------------------------------	----------

Respiratory, thoracic and mediastinal disorders

Acute respiratory failure	Adult respiratory distress syndrome	Alveolitis allergic
Asphyxia	Bronchospasm	Laryngeal oedema
Pulmonary fibrosis	Pulmonary haemorrhage	Pulmonary infarction
Pulmonary vasculitis	Respiratory arrest	Status asthmaticus
Pulmonary oedema		

Skin and subcutaneous tissue disorders

Angioneurotic oedema	Erythema nodosum	Pemphigus
Stevens-Johnson syndrome	Toxic epidermal necrolysis	Vascular purpura

Vascular disorders

Acute circulatory failure	Embolism	Malignant hypertension
Necrosis ischaemic	Thrombosis	

Status: Dec 2017

CTC = Common Toxicity Criteria also referred to as the Common Terminology Criteria for Adverse Events (CTCAE).

18.2 Algorithm for follow-up investigation of potential or suspected cases of drug-induced liver injury

If alanine aminotransferase or aspartate aminotransferase is >3 x the upper limit of normal, repeat the lab test within 48 hours to 72 hours. The test should be performed for aspartate aminotransferase, alanine aminotransferase, creatine kinase, total, direct and indirect bilirubin, alkaline phosphatase, lipase and gamma glutamyl transferase.

If alanine aminotransferase or aspartate aminotransferase is >3 x the upper limit of normal, (confirmed by retesting), and total bilirubin is ≥ 2 x the upper limit of normal, the investigator and the sponsor should discuss the following recommendations:

- Initiate a close observation of the subject/patient.
- Repeat testing of alanine aminotransferase, aspartate aminotransferase, alkaline phosphatase, total, direct and indirect bilirubin, creatine kinase, gamma glutamyl transferase, international normalized ratio, eosinophilic granulocytes and lipase 2 times to 3 times weekly.
- Decrease the frequency of retesting to once a week or less if abnormalities stabilize or if the IMP has been discontinued.

If aspartate aminotransferase or alanine aminotransferase is >3 x the upper limit of normal and total bilirubin is >2 x the upper limit of normal, the investigator and the sponsor should discuss following recommendations:

- Repeat testing of alanine aminotransferase, aspartate aminotransferase, alkaline phosphatase, total, direct and indirect bilirubin, creatine kinase, gamma glutamyl transferase, international normalized ratio, eosinophilic granulocytes and lipase.
- Consult a hepatologist/gastroenterologist who must then conduct an obligatory abdominal ultrasound and other examinations (e.g., liver biopsy) as necessary.
- Obtain more detailed history of symptoms (fatigue, nausea, vomiting, right upper quadrant pain or tenderness, fever, rash, and/or eosinophilia [$>5\%$]).
- Obtain history of concomitant medications, including herbal drugs, alcohol use or other drugs of abuse.
- As appropriate, conduct laboratory investigations for other possible causes of liver injury. Testing can be discussed with the sponsor.

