12.4 Collection of safety data

The following safety data will be collected: adverse events, vital signs, 12-lead ECGs, safety laboratory parameters, physical examination findings, and urine β -HCG pregnancy test outcome.

For the timings of assessments, see the schedules of events (Section 1.7).

Clinically relevant abnormal values (investigator's judgment) must be recorded as adverse events.

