Glucose		Calculated urinary albumin/creatinine ratio
Ketones		
Leukocyte esterase		
Nitrite		
pH		
Protein		
Urobilinogen		

If the dipstick test is positive except for pH, glucose or ketones and erythrocytes/leukocytes in menstruating subjects, a microscopic examination of urine sediment will be performed to determine the presence of erythrocytes, leukocytes, epithelial cells, crystals, casts, bacteria, and other findings.

The number of samples and volume per sample collected from each subject for safety laboratory analysis are given in [Table 3](#).

If laboratory values of liver parameters exceed pre-defined ranges (a combination of alanine aminotransferase and/or aspartate aminotransferase greater than 3 times the upper limit of normal and/or bilirubin greater than 2 times the upper limit of normal) after first application of IMP, a standard algorithm to detect and follow-up on potential severe cases of drug-induced liver injury will be applied (see Section 18.2).

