### 15.2.1 Laboratory parameters

Continuous and categorical laboratory parameters will be analyzed as described in Section 15.2 with individual specifications outlined in Table 2. The display of continuous laboratory parameters

will be by parameter group (clinical chemistry, clotting, hematology, and urinalysis). Categorical urinalysis parameters will be additionally classified as normal or abnormal.

Central laboratory parameters will be analyzed as described in the following paragraphs. No statistical analysis of local laboratory assessments, pregnancy tests, and drugs of abuse tests will be done. In general, all central laboratory parameters will be reported using Système International d'Unités (SI) units. Selected parameters will additionally be reported using US conventional units to facilitate safety data review (Section 19.4). The corresponding analyses of these parameters will be repeated using values in US conventional units.

Subjects potentially qualifying for Hy's law criteria (FDA 2009), i.e., subjects showing post-baseline abnormal hepatic values, will be presented in a separate listing. Subjects fulfilling the following 2 criteria potentially qualify for Hy's law:

- ALT > 3x ULN or AST >3x ULN.
- Total bilirubin > 2x ULN.

Table 2: Analysis of laboratory parameters

Parameter group	Parameter	Table of descriptive statistics	Frequency table (low/high)	Shift table	Mean plot	Shift plot
Clinical chemistry parameters (continuous)	Albumin	X	X	X		
	Alkaline phosphatase	X	X	X	X	X
	ALT	X	X	X		
	AST	X	X	X		
	Bilirubin	X	X	X		
	Calcium (albumin-corrected)	X	X	X	X	X
	Creatine phosphokinase	X	X	X		
	Creatinine	X	X	X	X	X
	Estimated GFR	X	X	X		
	GGT	X	X	X		
	Glucose	X	X	X		
	LDH	X	X	X		
	Magnesium	X	X	X		
	Parathyroid hormone	X	X	X		
	Phosphate	X	X	X		
	Potassium	X	X	X		
Protein	X	X	X			

Parameter group	Parameter	Table of descriptive statistics	Frequency table (low/high)	Shift table	Mean plot	Shift plot
	Sodium	X	X	X		
	Tricylglycerol lipase	X	X	X		
	Urea	X	X	X		
	Uric acid	X	X	X		
	Vitamin D	X	X	X		
Hematology parameters (continuous)	Hematocrit	X	X	X		
	Hemoglobin	X	X	X		
	Platelet count	X	X	X		
	RBC	X	X	X		
	WBC	X	X	X		
Urinalysis parameters (continuous)	pH	X	X	X		
	Albumin (microalbumin)	X	X	X		
	Creatinine	X	X	X		
	Urinary albumin/creatinine ratio (semi-quantitative dipstick)	X	X	X		
	Calculated urinary albumin/creatinine ratio (central laboratory)	X	X	X		
Urinalysis parameters (categorical)	Bilirubin	X		X		
	Blood	X		X		
	Glucose	X		X		

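### As printed, a confirmed ALT/AST rise above 3 × ULN with bilirubin below 2 × ULN has no liver-algorithm step after the 48 to 72 h repeat test

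*Protocol*

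**What the plan says.** Protocol Section 12.4.5 (Safety laboratory) applies the liver-injury algorithm, after first IMP, to results described as "a combination of alanine aminotransferase and/or aspartate aminotransferase greater than 3 times the upper limit of normal and/or bilirubin greater than 2 times" (both multiples refer to ULN). With and/or in both places, an isolated transaminase rise enters.

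Section 18.2 then has three conditional steps:

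- **Repeat test.** Any ALT or AST above 3 × ULN is retested within 48 to 72 hours. Besides the two transaminases the repeat covers "creatine kinase, total, direct and indirect bilirubin, alkaline phosphatase, lipase and gamma glutamyl transferase". INR is not in it, nor in the scheduled panel of Section 12.4.5.
- **Lower tier.** If ALT or AST "is >3 x the upper limit of normal, (confirmed by retesting), and total bilirubin is ≥ 2 x the upper limit of normal", investigator and sponsor should discuss close observation and retesting of a longer list that includes INR, "eosinophilic granulocytes and lipase 2 times to 3 times weekly". The step-down is: "Decrease the frequency of retesting to once a week or less if abnormalities stabilize or if the IMP has been discontinued".
- **Upper tier.** The condition reads: "If aspartate aminotransferase or alanine aminotransferase is >3 x the upper limit of normal and total bilirubin is >2 x the upper limit". In that case they should discuss a further repeat, a hepatology or gastroenterology consultation with ultrasound, a fuller history and a search for other causes. This tier does not ask for confirmation by retesting and sets no retest frequency.

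SAP Section 15.2.1 screens for Hy's law with ALT or AST above 3 × ULN together with "Total bilirubin > 2x ULN", the same bilirubin limit as the upper tier.

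**The concern.** A two-tier scheme normally sends milder cases to monitoring and more serious ones to specialist work-up. Here both tiers require raised bilirubin, and at practically the same level. The milder tier has almost no bilirubin range of its own, and the group it would be expected to serve, a confirmed transaminase rise without that bilirubin rise, belongs to neither. Since the upper limit coincides with the SAP's Hy's law screen, the lower tier was probably meant for cases below it.

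An isolated transaminase elevation can precede a combined one. For such a subject the algorithm gives no prompt for close observation, for frequent retesting or for INR once the repeat is back.

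The setting gives the algorithm some weight. Table 2 in Section 9.3.2 has no liver-enzyme rule for stopping IMP. Section 1.4.2 requires acetaminophen about every 6 hours for 72 hours after the first infusion of each treatment period. Exclusion criterion 16 admits subjects with ALT or AST up to 2 × ULN, for whom a 3/2 = 1.5-fold rise reaches the 3 × ULN limit.

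**Working it through.** The plan gives no figure to reproduce. The check is of logic, followed by a range for what is lost.

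**1. Steps triggered.** Take a confirmed ALT of 4 × ULN, vary total bilirubin, and apply the conditions of Section 18.2 with the lower-tier sign as printed (≥) and with ≤ in its place.

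| Bilirubin (× ULN) | Lower tier ≥ 2 (printed) | Lower tier ≤ 2 |
|---|---|---|
| 0.8 | repeat only | repeat + close observation |
| 1.5 | repeat only | repeat + close observation |
| 1.99 | repeat only | repeat + close observation |
| 2.0 | repeat + close observation | repeat + close observation |
| 2.01 | repeat + close observation + specialist | repeat + specialist |
| 3.0 | repeat + close observation + specialist | repeat + specialist |

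As printed, everything below 2 × ULN stops at the repeat, and only exactly 2 × ULN is handled by the lower tier alone. With ≤ there is neither gap nor overlap. A strict < would leave exactly 2.0 × ULN without a tier.

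**2. Is the sign credible?** Some inequality signs did not survive reading from the PDF: an exclamation mark before 300 kPa in Sections 1.5.3.2 and 14.1.7.2, where SAP Section 13.2.4 has ≤, and ∇ before the eGFR limits in Table 2. These are nonsense characters, not clean signs reversed. Clean signs agree with the wording elsewhere: ≥ 4 in Section 7 matches inclusion criterion 4, and ≤ 2 years in Section 8.1.1 matches inclusion criterion 3. The ≥ is therefore taken as written, but that is inference.

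**3. Tests not prompted.** Use 28 days = 4 weeks, the lower tier's 2 to 3 tests per week, and 0 to 1 per week after step-down.

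- No step-down: 4 × (2 to 3) = 8 to 12.
- Step-down after week 1: (2 to 3) + 3 × (0 to 1) = 2 to 6.
- Step-down at once: 4 × (0 to 1) = 0 to 4.

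The first line needs values that never stabilize and IMP not counted as discontinued. The plan does not say whether planned completion of dosing on Day 10 counts as discontinuation.

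**4. What scheduled sampling already gives** (nominal days, visit windows ignored).

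- Period A, after the first infusion day: Days 4, 7, 10, 15 = 4 samples in 14 days = 2.0 per week.
- Period B: Days 186, 189, 192, 197 = 4 in 14 days = 2.0 per week.
- The prompt would add (2 to 3) − 2.0 = 0 to 1 test per week in these windows.
- After Day 15 the next scheduled samples are Days 43, 85 and 155 (none at Visit 9): gaps of 28, 42 and 70 days.
- After Day 183 without Period B, the next are Days 253 and 365: gaps of 70 and 112 days.

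The loss therefore concerns mainly cases first seen at Visit 6, at Visit 15 or later.

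**The case against.** **The sign may be a reading error.** Everything turns on one character in a text where others are corrupt, and the argument from the plan's own logic makes ≤ the more sensible source sign. This stands as a reason for limited confidence and for checking the PDF first. It does not show that the sign was misread.

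**The repeat step could loop.** It has no bilirubin condition and does not say once only. A retest still above 3 × ULN meets it again, which would mean testing every 2 to 3 days, or 7/3 to 7/2 = 2.3 to 3.5 times a week. The words about confirmation by retesting in the next step, however, mark the repeat as a single confirmation.

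**The overlap above 2 × ULN may be deliberate.** The tiers also differ in that only the lower one requires confirmation, so they could work cumulatively: specialist work-up at once, monitoring once confirmed. That is tenable, and overlap alone is no defect. It does not supply a step for subjects below 2 × ULN.

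**Isolated rises have general cover, and the algorithm is aimed at potentially severe cases.** Under Section 12.4, clinically relevant abnormal values "must be recorded as adverse events". Section 12.4.1 has them followed to resolution or stability, Section 12.4.5 requires a comment on alert-range values, and Section 9.3.2 lets the investigator stop IMP. Both tiers are worded as should, which Section 3.2 defines as not mandatory. All this stands and keeps the point minor. None of it sets a retest frequency or asks for INR, and Section 12.4.5 does send isolated rises into the algorithm.

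**Conclusion.** The algorithm is wrong as printed: a confirmed ALT or AST above 3 × ULN with bilirubin below 2 × ULN has no step after the repeat test. Severity is minor. The loss is a recommendation, worth 0 to 12 tests over 28 days depending on when the step-down applies, and 0 to 1 test per week inside the dosing windows. The documents give no expected number of such subjects, so a trial-wide figure cannot be stated. Endpoints, power and type I error are not affected.

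Confidence is medium. The conclusion assumes that ≥ is the sign in the PDF and that the 48 to 72 hour repeat is a single confirmation.

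**What to change.** Check the lower-tier bilirubin sign in Section 18.2 against the PDF. If it is ≥, change it in the next amendment to ≤ 2 × ULN and leave the upper tier at > 2 × ULN, so that every confirmed ALT or AST above 3 × ULN falls into exactly one tier.

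In the same edit, write close observation and retesting two to three times a week, with the same step-down, into the upper tier. Subjects above 2 × ULN now get these only through the overlap and would otherwise lose them.

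The cost is one sign and one phrase in an appendix. The downside is a few extra retests in subjects whose transaminases are already raised, using tests that Section 18.2 lists. If the PDF already has ≤, only the upper-tier frequency wording remains, and it is optional.

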18.3 Subject-reported outcomes

The subject-reported outcomes provided in the following sections are validated English samples.

18.3.1 Patient Global Impression of Change

DMS version: 1.0

ID: 1029120

PATIENT GLOBAL IMPRESSION OF CHANGE (PGIC)

Since the start of the study, my overall status is:

✓ *one box only:*

- [1] Very Much Improved
- [2] Much Improved
- [3] Minimally Improved
- [4] No Change
- [5] Minimally Worse
- [6] Much Worse
- [7] Very Much Worse

(US/English)

18.3.2 Patient Global Impression of Severity

Please choose the response below that best describes the severity of your CRPS symptoms over the past week:

- ~ None
- ~ Mild
- ~ Moderate
- ~ Severe
- ~ Very severe

18.3.3 EuroQol-5 dimension-5 level

DMS version: 1.0

ID: 1028200

Health Questionnaire

English version for the UK

DMS version: 1.0

ID: 1028200

Under each heading, please tick the ONE box that best describes your health TODAY

MOBILITY

- I have no problems in walking about
- I have slight problems in walking about
- I have moderate problems in walking about
- I have severe problems in walking about
- I am unable to walk about

SELF-CARE

- I have no problems washing or dressing myself
- I have slight problems washing or dressing myself
- I have moderate problems washing or dressing myself
- I have severe problems washing or dressing myself
- I am unable to wash or dress myself

USUAL ACTIVITIES (e.g. work, study, housework, family or leisure activities)

- I have no problems doing my usual activities
- I have slight problems doing my usual activities
- I have moderate problems doing my usual activities
- I have severe problems doing my usual activities
- I am unable to do my usual activities

PAIN / DISCOMFORT

- I have no pain or discomfort
- I have slight pain or discomfort
- I have moderate pain or discomfort
- I have severe pain or discomfort
- I have extreme pain or discomfort

ANXIETY / DEPRESSION

- I am not anxious or depressed
- I am slightly anxious or depressed
- I am moderately anxious or depressed
- I am severely anxious or depressed
- I am extremely anxious or depressed

[figure not shown]
DMS version: 1.0

ID: 1028200

- We would like to know how good or bad your health is TODAY.
- This scale is numbered from 0 to 100.
- 100 means the best health you can imagine.
0 means the worst health you can imagine.
- Mark an X on the scale to indicate how your health is TODAY.
- Now, please write the number you marked on the scale in the box below.

YOUR HEALTH TODAY =

The best health
you can imagine

The worst health
you can imagine

18.3.4 PROMIS-29 profile version 2.0

PROMIS-29 Profile v2.0

Please respond to each question or statement by marking one box per row.

Physical Function		Without any difficulty	With a little difficulty	With some difficulty	With much difficulty	Unable to do
PFA11 1	Are you able to do chores such as vacuuming or yard work?.....	 5	 4	 3	 2	 1
PFA21 2	Are you able to go up and down stairs at a normal pace?.....	 5	 4	 3	 2	 1
PFA28 3	Are you able to go for a walk of at least 15 minutes?.....	 5	 4	 3	 2	 1
PFA53 4	Are you able to run errands and shop?	 5	 4	 3	 2	 1
Anxiety		Never	Rarely	Sometimes	Often	Always
EDANX01 5	I felt fearful.....	 1	 2	 3	 4	 5
EDANX40 6	I found it hard to focus on anything other than my anxiety	 1	 2	 3	 4	 5
EDANX41 7	My worries overwhelmed me.....	 1	 2	 3	 4	 5
EDANX53 8	I felt uneasy	 1	 2	 3	 4	 5
Depression		Never	Rarely	Sometimes	Often	Always
EDDEP04 9	I felt worthless	 1	 2	 3	 4	 5
EDDEP06 10	I felt helpless.....	 1	 2	 3	 4	 5
EDDEP29 11	I felt depressed.....	 1	 2	 3	 4	 5
EDDEP41 12	I felt hopeless.....	 1	 2	 3	 4	 5
Fatigue		Not at all	A little bit	Somewhat	Quite a bit	Very much
H17 13	I feel fatigued	 1	 2	 3	 4	 5
AN3 14	I have trouble starting things because I am tired.....	 1	 2	 3	 4	 5

PROMIS–29 Profile v2.0

Fatigue

In the past 7 days...

		Not at all	A little bit	Somewhat	Quite a bit	Very much
FATEXP41 15	How run-down did you feel on average? ...	 1	 2	 3	 4	 5
FATEXP40 16	How fatigued were you on average?	 1	 2	 3	 4	 5

Sleep Disturbance

In the past 7 days...

		Very poor	Poor	Fair	Good	Very good
Sleep109 17	My sleep quality was.....	 5	 4	 3	 2	 1

In the past 7 days...

		Not at all	A little bit	Somewhat	Quite a bit	Very much
Sleep116 18	My sleep was refreshing.....	 5	 4	 3	 2	 1
Sleep20 19	I had a problem with my sleep	 1	 2	 3	 4	 5
Sleep44 20	I had difficulty falling asleep	 1	 2	 3	 4	 5

Ability to Participate in Social Roles and Activities

		Never	Rarely	Sometimes	Usually	Always
SRPPER11 _CaPS 21	I have trouble doing all of my regular leisure activities with others.....	 5	 4	 3	 2	 1
SRPPER18 _CaPS 22	I have trouble doing all of the family activities that I want to do	 5	 4	 3	 2	 1
SRPPER23 _CaPS 23	I have trouble doing all of my usual work (include work at home)	 5	 4	 3	 2	 1
SRPPER46 _CaPS 24	I have trouble doing all of the activities with friends that I want to do	 5	 4	 3	 2	 1

Pain Interference

In the past 7 days...

		Not at all	A little bit	Somewhat	Quite a bit	Very much
PAININ9 25	How much did pain interfere with your day to day activities?.....	 1	 2	 3	 4	 5
PAININ22 26	How much did pain interfere with work around the home?	 1	 2	 3	 4	 5
PAININ31 27	How much did pain interfere with your ability to participate in social activities?.	 1	 2	 3	 4	 5
PAININ34 28	How much did pain interfere with your household chores?.....	 1	 2	 3	 4	 5

PROMIS–29 Profile v2.0

Pain Intensity

In the past 7 days...

Global07 29	How would you rate your pain on average?.....											
		0	1	2	3	4	5	6	7	8	9	10
		No pain										Worst imaginable pain

